identified by Palmetto Health Physical Therapists will be provided information about the study verbally by a USC research staff member. Interested patients will be able to ask questions and read the consent form. They will have the opportunity to complete the informed consent process either at the first or second outpatient physical therapy appointment.

b. Inclusion and Exclusion Criteria

After initial identification of potential patient participants by physical therapists, research staff will screen patients for eligibility criteria in-person or over the telephone.

Inclusion criteria:

Eligible participants will 1) be 40-79 years of age, 2) have had a knee replacement in the last 2 months, 3) be willing to wear an accelerometer for 7 days during assessments, and 4) be English speaking.

Exclusion criteria:

As all patients will be under physicians' supervision post-TKR, participants will only be excluded if they (1) have any contraindications to activity, (2) have a mobility limiting comorbidity (e.g. spinal stenosis), or (3) have a scheduled surgery (i.e., TKR on contralateral knee) within the next 6 months.

c. Local Number of Subjects

We will aim to randomize 50 patients that had a knee replacement within the last 2 months and are attending outpatient physical therapy at the Palmetto Health USC Orthopedic Center. We anticipate that we will need to approach and screen approximately 75 patients to enroll our goal of 50 patients.

d. Study-Wide Number of Subjects

NA

e. Study Timelines

Subject participation will last 12 weeks. We estimate it will take 15 months to complete the study, which will include finished study enrollment, data collection and data analysis (See Figure 1).

Figure 1. Project Timeline

	Project Month														
	1	2	3	4	5	6	7	8	9	10	11	12	13	14	15
Finalize protocol & IRB approval	X	X	X												
Recruit TKA patients (n=50)				X	X	X	X	X	X	X	X	X	X		
Intervention				X	X	X	X	X	X	X	X	X	X		
Completing 12 week assessments				X	X	X	X	X	X	X	X	X	X	X	
Data Analysis														X	X
Prepare manuscript & presentations														X	X
Draft & submit NIH R21 or R01														X	X

f. Study Endpoints

[figure not shown]

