- Self-reported exercise identity will be assessed at baseline and 12-week assessments using the Self-Reported Exercise Identity Scale.³³ Participants will rate on a scale from 1 (strongly disagree) to 5 (strongly agree) their feelings relating to exercise identity. Examples include, “I would feel a real loss if I were forced to give up exercising” and “I need exercise to feel good about myself.”

g. Procedures Involved

Design Overview: We propose to conduct a pilot two-arm cluster randomized controlled trial with patients attending outpatient physical therapy following TKR. The proposed project was developed in collaboration with [name], Senior Physical Therapist at Palmetto Health USC Orthopedic Center. Over 9 months, TKR patients (n=50) attending outpatient physical therapy at Palmetto Health USC Orthopedic Center will be recruited and randomized to either 1) PATH-12 (control), or 2) PATH. Due to potential contamination of the intervention between patients in PATH-12 and PATH during typical open, group-like physical therapy settings, we have opted to randomize physical therapy sites instead of individual patients. Specifically, physical therapy sites will be randomized to either Immediate or Delayed. The first phase of the study will take place starting in November and end after 25 participants have been recruited. During this time, those sites randomized to Immediate will receive the PATH intervention and those sites randomized to Delayed will receive the PATH-12 intervention. There will then be a “wash out period” to allow for all the participants to finish their current PT. After this “wash out period”, the second phase of the study will begin and will end after 25 participants have been recruited. During this time, those sites randomized to Immediate will receive the PATH-12 intervention and those sites randomized to Delayed will receive the PATH intervention.”

Screening: Participants will be required to complete a brief screening after the first physical therapy appointment. Research staff will administer the screening in-person or over the telephone. The screening will assess eligibility criteria and willingness to participate. Following the completion of the screener, eligible and interested participants will be invited to complete the informed consent process.

Randomized Conditions:

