Treatment Fidelity. Due to the open, group-like nature of physical therapy and patient confidentiality, we are unable to audio record treatment sessions. Therefore, to monitor treatment fidelity to ensure intended session content for both conditions is delivered and that unintended session content (i.e., contamination such as goal setting on physical activity levels with a patient randomized to PATH-12) is not delivered, physical therapists will complete a session checklist. In addition, random observations will occur by USC research staff. The physical therapist and observation fidelity checklists will monitor session duration, goals set, and indication if aerobic physical activity was discussed.

h. Data and Specimen Banking

NA

i. Statistical Analysis

Descriptive statistics will be used to describe baseline characteristics, establish recruitment and retention rates, and examine intervention intensity (session frequency, duration, and fidelity) and patient and therapist satisfaction. Mixed ANOVA or ANCOVAs, if appropriate adjustments are required based on baseline characteristics, will examine the changes in physical activity levels (MVPA/week, steps/day), and pain (PROMIS and WOMAC) across time between PATH and PATH-12. Additionally, differences between PATH and PATH-12 in physical function (chair stands, Timed Up and Go, 6-minute walk) will be examined at 12 weeks. Although the proposed study may not be powered to detect significant differences, the results will allow us to collect feasibility and acceptability data, refine the intervention, if necessary, and determine effect sizes for future grant submissions.

j. Data Management

All surveys will be administered either on paper or online via REDCap (secure, web application for building and managing online surveys and databases – managed by the University of South Carolina). Paper surveys will be stored in a locked filing cabinet at Palmetto Health-USC Orthopedic Center or the TecHealth Center at University of South Carolina. All computer files will be password protected. Only the study team will have access to the data.

k. Confidentiality

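### Fifty patients cannot determine an effect size for the next grant; the plan should promise estimates with confidence intervals and size the next trial on a pre-stated important difference

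*Combined protocol and SAP*

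**What the plan says.** The last sentence of section 7(i) opens with a concession, "Although the proposed study may not be powered to detect significant differences", and then lists what the results will still provide: feasibility and acceptability data, refinement of the intervention, and the ability to "determine effect sizes for future grant submissions". The project timeline (section 7(e), Figure 1) carries a row "Draft & submit NIH R21 or R01" in months 14 and 15, alongside data analysis.

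The target in section 7(c) is 50 patients, with no calculation behind it. Section 7(g) describes the study as a two-arm cluster trial and says "we have opted to randomize physical therapy sites instead of individual patients". After the first 25 patients and a wash-out, the sites swap: "those sites randomized to Immediate will receive the PATH-12 intervention and those sites randomized to Delayed will receive the PATH intervention".

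The efficacy analysis is given as "Mixed ANOVA or ANCOVAs, if appropriate adjustments are required based on baseline characteristics". It names no site or phase term and no confidence interval for the between-arm difference. The documents also give no number of sites, intraclass correlation (ICC), dropout allowance or target difference, and no rule for how the pilot estimate would size the next trial. Section 7(f) makes feasibility and acceptability the primary endpoint.

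**The concern.** The sentence treats low power as a limit on significance testing only, and offers the effect size as something the study can still supply. The same standard error governs both. A sample too small to detect a moderate effect is also too small to locate it.

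What is at stake is the next application. If the observed difference became the planning effect, a chance overestimate would give a follow-on trial that is far too small, and a chance underestimate could make a worthwhile programme look not worth pursuing. Figure 1 puts the grant drafting in the same two months as the analysis, so the use is close at hand, and nothing in the plan guards against it.

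**Working it through.** **Inputs from the documents.** 50 patients (section 7(c)). The 12-week SDs in Table 1 under Preliminary Studies: steps/day 1687.8 (n=6) and 1653.2 (n=7); bouted MVPA 5.4 and 135.8 min/week.

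**Assumptions, because the documents are silent.** A 1:1 split, so 25 per arm, or 20 per arm after 20% loss; two-sided 5% level; 80% power for the next trial. There are no stated inputs from which the figure of 50 can be reproduced.

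**1. Precision of the effect size, ignoring clustering.** SE(d) = sqrt(2/n + d²/(4n)).
- n=25, d=0.5: sqrt(0.08 + 0.0025) = 0.287; half-width 1.96 × 0.287 = 0.56; 95% CI -0.06 to 1.06.
- n=20, d=0.5: SE 0.321; CI -0.13 to 1.13.
- n=25, d=0.3: SE 0.284; CI -0.26 to 0.86.

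**2. The same in raw units.** Half-width of a 12-week difference in means = 1.96 × SD × sqrt(2/25).
- Steps/day: 1.96 × 1653.2 × 0.283 = 916, and 936 with SD 1687.8. The 12-week means in Table 1 are 4255.6 and 4943.6.
- MVPA, on the larger SD: 1.96 × 135.8 × 0.283 = 75 min/week. The 12-week means are 3.5 and 62.1.

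Table 1 reports bouted MVPA from very small groups, whereas this plan uses total weekly MVPA, so the MVPA figure is only a guide.

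**3. What this does to the next trial's size.** n per arm = 2 × ((1.96 + 0.84)/d)² + 1, individually randomised.

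| Planning effect d | n per arm |
|---|---|
| 1.06 (upper limit when 0.5 is observed) | 15 |
| 0.5 | 64 |
| 0.2 | 394 |
| Lower limit (-0.06) | none exists |

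If the truth is 0.5 and the pilot shows 1.06, 15 per arm has about 26% power. If the pilot shows 0.5 and the truth is 0.2, 64 per arm has about 20% power. If the truth is 0.3, the pilot shows a zero or negative difference with probability Φ(-0.3/0.284), about 15%.

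**4. How much clustering adds.** For sites that swap condition, design effect = 1 + (m-1)ICC - m × ICC × CAC, where m is patients per site per phase and CAC is the correlation of a site's effects between phases. All values here are assumed.
- 4 sites (m=6.25), ICC 0.05: 1.2625 - 0.3125 × CAC, which is 1.11 at CAC 0.5 and 0.95 at CAC 1. A parallel cluster design would give 1 + 11.5 × 0.05 = 1.58.
- 2 sites (m=12.5), ICC 0.10, CAC 0.5: 1 + 1.15 - 0.625 = 1.53. At a design effect of 1.5 the interval around 0.5 widens to -0.19 to 1.19.

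**5. What the pilot can estimate better.**
- SD of a roughly normal outcome: on 48 degrees of freedom the limits are ×0.83 to ×1.25, so the sample size changes by 0.83² = 0.69 to 1.25² = 1.56. That is tolerable for planning.
- SD of MVPA: both Table 1 SDs exceed their means. Simulating 25 per arm with mean 62.1 and SD 135.8 in both arms, the central 95% of pooled SDs runs from about 0.4 to 1.7 times the truth (gamma) or 0.3 to 2.2 times (lognormal).
- Between-site SD, even if site means were observed directly: limits ×0.57 to ×3.7 with 4 sites, ×0.45 to ×32 with 2.

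**The case against.** The best defence is that this is openly a pilot. The primary endpoint is feasibility, the stated aim is preliminary efficacy, the sentence itself concedes limited power, and effect sizes come last among three listed uses. If the verb is read loosely as estimating, most of the complaint goes. This stands as a reason to rate the point low. It does not remove it, because the concession covers significance testing only and no interval is planned that would show the reader how loose the estimate is.

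A reader might infer three stronger things that the documents do not support.

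- **That the next trial will be mis-sized, or the programme dropped.** The plan contains no sizing rule and no stop/go rule. It does not say the point estimate will be used, or used alone, so the harm is conditional.
- **That site randomisation makes the imprecision much worse.** Sites swap conditions, so each acts as its own control. Under most of the assumed values the penalty is small; it becomes material only with very few sites, a high ICC and weak correlation between phases.
- **That the pilot gives a poor effect size but a dependable SD, correlation and between-site variance.** This is defensible for the SD of steps/day. It fails for MVPA and for site variance, as step 5 shows. A baseline to 12-week correlation of 0.5 from 50 patients would itself have a 95% CI of about 0.26 to 0.68.

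Adjusting for baseline would narrow the interval, but an assumed correlation of 0.5 multiplies the half-width by sqrt(1 - 0.25) = 0.87, a gain of 13%.

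**Conclusion.** The point holds, as a minor one. The plan claims a property that 50 patients do not confer: with about 25 per arm, the 95% half-width is about 0.56 SD, or some 920 to 940 steps/day. For an observed 0.5, planning at the upper limit instead of the point estimate cuts the next trial more than four-fold (64/15 = 4.3), and the lower limit gives no usable size. This rests on a 1:1 split, approximate normality, no baseline adjustment and no clustering penalty; 20% loss or a material site effect would widen the interval.

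The conduct of this trial and its primary feasibility endpoint are not affected. The consequence falls on the next application, and only if the point estimate is taken as its planning effect.

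**What to change.** In section 7(i), replace the phrase about determining effect sizes with text such as:

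> Estimate between-arm differences with 95% confidence intervals from a model that includes site and phase. These point estimates will not be used alone as the planning effect. The next trial will be sized on a pre-stated important difference (for example in steps/day), with the pilot informing recruitment, retention and a conservative (upper-limit) SD, each with its 95% confidence interval.

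For MVPA, work on a transformed scale or give a bootstrap interval for the SD, because the data are likely to be strongly skewed. Do not promise a between-site variance or ICC usable for planning. State the number of sites so that the reader can judge this.

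The cost is a change of wording and a few extra intervals, with no new data, patients or procedures. The real downside is that the sponsor must justify a target difference in the next application and cannot simply borrow the pilot's.
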